5.7 Withdrawal of Subjects

This is not a treatment study; withdrawing or being terminated from this study will not have an impact on participant safety. A study clinician or the PI may withdraw a participant without their consent if he or she feels that it is not in a participant's best interest to continue in the study or the person is unable to complete the study procedures. All data previously collected from participants who withdraw or are withdrawn will be kept and may be used in the study data analysis. Participants may withdraw at any time by informing the Research Coordinator and/or the PI. If a participant wants to withdraw or we choose to withdraw a participant, while she/he are using study equipment (i.e., one of the prostheses) we will arrange for the study prosthesis to be returned/removed and the participant's as-prescribed prosthesis to be re-fit.

6.0 Reporting

All safety information on AEs, SAEs, unanticipated events or problems, and protocol deviations will be collected. This information will be collected at study visits and whenever subjects call to report a problem. The information will be collected on VA IRB forms (Report of a SAE and/or Problem Form, or Report of Problems (ROP) Form) and in AE log forms as needed. Safety data will be collected on an as-needed basis and will begin upon enrollment into the study. All safety reporting requirements will be followed. Any anticipated AEs will be recorded on a log sheet and reported annually with the CRQ.

If we become aware of relevant findings or information that may affect subjects' health or welfare, we will contact subjects by phone and/or a letter to notify them.

7.0 Information Security, Privacy, and Confidentiality

As with any study, it is possible, although unlikely given the impersonal nature of the data collected, that participants may experience a loss or invasion of privacy or confidentiality because of participation in this study. The risk of harm is minimal and the protections described here will be followed.

Electronic data with PHI/sensitive information will be stored on the secure server at the VA Puget Sound. These data will only be accessed by authorized study personnel. Hardcopies of VA sensitive data and documents with PHI will be stored in a locked file cabinet in a locked office at the VA Puget Sound (Seattle). Study files/data with PHI or sensitive information will not be sent off-site. This is a locked facility to which only study investigators have access. Identifiable data will not be transmitted, transported, or stored on portable media or laptops outside of the VA, and the data will only be accessed by authorized VA study staff. We will notify the Information Security Officer of the location of the hardcopy data/files via the Data Inventory form. If study data is improperly used or disclosed we will notify the ISO and Privacy Officer within one hour of becoming aware of the issue.

Study staff will only have access to the minimum necessary identifiable information needed to perform their role. Study staff that depart the VA or are removed from the research team will be promptly removed from the research application and will no longer have access to sensitive study data.

Study data will be labeled with a study assigned code and de-identified data sets will be created/used when data is made publicly available and transmitted without restriction. A copy of de-identified data will also be made available to public search, retrieval, and analysis per the limitations the Data Management Access Plan (DMAP). The key to the code will be stored separately from the study data, and only designated VA study staff will have access to it.

De-identified, non-sensitive electronic data labeled with the study assigned codes, and all 18 HIPAA identifiers removed or converted to de-identified format, may be stored on password-protected equipment (computers/laptops/sd cards) but will not be encrypted. De-identified data files may be sent off-site via email, file transfer software, and/or other electronic media (CD/DVD, usb drive) to our biostatistician, off-site collaborators, and between study investigators.

Any consented photography or video will protect participants' identity (e.g., by obscuring the subject's face and any identifying marks like tattoos). The videos and photos may include the participant's entire body, but they will be anonymized during data processing; the participant's face will be blurred, any identifying marks will be covered or blurred, and then the original file will be deleted. If a participant's voice is accidentally recorded, that section of video would be altered prior to any use outside of the VA study team. The video camera and the recording media (e.g., SD cards, optical disks) will be stored in a locked office at the VA Puget Sound. Photos and videos that do not contain identifiable information may also be stored on password-protected computers for future use in scientific presentations and publications.

Study records with PHI/PII will be destroyed using VA approved procedures and in accordance with the records retention schedule after the study is completed. Hard copy data with identifiable and/or sensitive information will be shredded per VA approved policies. Electronic data containing identifiable information will be wiped using VA approved software. De-identified data will be stored indefinitely.

8.0 Communication Plan

This is not a multi-site study. If students or staff at the University of Washington are participating as study staff at the VA, the PI will assure that the appropriate approval is obtained from the UW Human Subjects Division.

Title: Pivot-Flex Foot: Optimal Coupling Ratio Between Transverse and Sagittal-plane Motions Using a Torsionally Adaptive Prosthesis for Individuals With Lower Limb Amputation

NCT03532100

Document Date: 23Sep2025

Statistical Analysis Plan

Linear mixed effects regression was used to test for an association between each outcome (dependent variable) by coupling ratio. Coupling ratio was the independent fixed effect (modeled as categorical using 4 dummy variables). Study participant and study participant by coupling ratio interaction were random effects. To address the variability in outcome variance among participants, maximum penalized likelihood estimation was used (Chung 2013). Hypothesis testing for the association between outcome and coupling ratio was carried out using conditional F-tests with degrees of freedom estimated using the Kenward-Roger method. Pairwise hypothesis testing was carried out with adjustments for multiple comparisons using Tukey's method. Results are summarized as outcome means (\pm standard error) by coupling ratio, and pairwise mean differences in outcome by coupling ratio category accompanied by standard errors and 95% confidence intervals (CI). Analyses were carried out using R 4.2.1 (Team RC, 2022), and packages tidyverse, lme4, blme and emmeans (Chung, 2013; Wickham, 2019; Bates, 2015; Lenth, 2022). Statistical analysis on satisfaction results were not performed due to the small sample size and the higher expected variances in qualitative data.

Team RC. R: A language and environment for statistical computing [Internet]. Vienna, Austria: R Foundation for Statistical Computing; 2022. Available from: www.R-project.org

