3.0 Specific Aims and Hypotheses

(1) To identify the optimal coupling (pairing) ratio between transverse plane (*horizontal rotation*)- and sagittal plane (*flexing forward and backward*) motions using a novel, torsionally adaptive prosthesis (TAP). Our *general hypotheses* are:

(H1) a coupling ratio exists between 0 (no coupling) to 1:2 (1° transverse-plane motion for every 2° sagittal-plane motion) that minimizes transverse-plane socket torque

(H2) an amputee preferred coupling ratio will exist within this range. We will use the results of this experiment to specify the coupling ratio of the Pivot-Flex Foot used in specific aim 2.

(2) To determine if a passive prosthesis with an optimal coupling ratio (Pivot-Flex Foot) can reduce transverse-plane socket torque and compensatory gait biomechanics when compared to a standard-of-care prosthetic foot. Our *general hypotheses* for the different ambulatory activities are:

(H3) the peak transverse-plane socket torque will be significantly different between the Pivot-Flex Foot and the standard-of-care prosthetic foot

(H4) the positive sagittal-plane work done at the hip joint will be significantly different between the Pivot-Flex Foot and the standard-of-care prosthetic foot

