The TAP's five settings will be tested in a randomized order. The first setting will be selected then participants will be asked to walk around a ~3-foot radius circle several (3-6) times at their SSWS. Participants will be asked to do the circle walking tests in both clockwise and counter-clockwise directions (randomized order). Once we have enough data, participants will be asked to rate their satisfaction with the setting on a 0-10 scale. The same process will be repeated for each of the remaining settings.

After all five settings have been tested the research prosthetist will re-fit the participants' as-prescribed prosthesis. We will schedule the next study visit before participants leave or we will call them later to schedule it.

Part 2: Build and evaluate the PFF

Informed by the results of Part 1, we will design, build and thoroughly bench test our PFF. We will build the PFF in a few sizes, and in left and right foot configurations to accommodate for participant variability. When ready, we will test the PFF with participants as described below.

Visits and length of participation

Consent and data collection procedures will be done at the VA Puget Sound in Seattle and participants will wear study assigned prostheses at home/in the community. Participants will be asked to do three visits that may last up to 4 hours each. If we find that data are missing or corrupt participants may be asked to do another study visit. All procedures are for research purposes and provide no clinical treatment. Participants will be provided rest breaks throughout the procedures, and may request one at any time. We may call and/or email participants to remind them about upcoming study visits.

Visit 1

Eligibility

Participants' residual limb, prosthesis, and fitment will be examined to determine if they can participate in the study. The research prosthetist may adjust their prosthesis to optimize fitment. If a participant is unable to continue in the study they will be compensated for their effort.

Demographic Information *If a participant completed Part 1 of the study then we will not collect this information again.*

We will ask participants to provide us with the following required demographic information:

- Sex
- Race
- Ethnicity
- Veteran status

We will ask participants to provide us with the following study demographic information:

- Age
- Years since amputation
- Level and side of amputation
- Cause of amputation
- Body weight
- Height

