Satisfaction data from the experiment will be tabulated for straight and both directions of the circle walking trials at the five different coupling ratios (0, 1:6, 1:4, 1:3, and 1:2). This data will be processed and aggregated using project specific software (Matlab; Mathworks, Natick, MA).

We hypothesize that:

H2.1: When walking in a straight line, there exists a coupling ratio that maximizes satisfaction.

H2.2: When circle walking with the prosthetic limb on the inside of the turn, there exists a coupling ratio that maximizes satisfaction.

H2.3: When circle walking with the prosthetic limb on the outside of the turn, there exists a coupling ratio that maximizes satisfaction.

The statistical analysis to test these hypotheses (H2.1, H2.2, and H2.3) will require three Friedman analyses of variance (ANOVA). These analyses will test for differences between the five coupling ratios across the three different ambulatory activities. The experiment-wise significance will be set a priori at an alpha level of $p<0.05$ and a Bonferroni adjustment will be applied for multiple comparisons. All analyses will be performed using existing VA enterprise software (SPSS Statistics v22; IBM, Inc.). Exact p-values will be reported for each test.

The results of testing hypothesis 1 will be used to define the optimal coupling ratio. The coupling ratios (0, 1:6, 1:4, 1:3, and 1:2) will be placed in rank order and an evenly weighted rank average will be used to identify the coupling ratio that minimizes the transverse-plane moment. If this algorithm cannot distinguish between two or more coupling ratios, then a similar method will be used to rank the results from hypothesis 2. If neither algorithm can distinguish the optimal coupling ratio, then the investigative team will engage the clinical

team and use their experience to select a coupling ratio for use in specific aim 2. Please see our discussion of this issue in the potential problems section.

Specific Aim 2: Kinematic and kinetic data from the experiment will be analyzed to identify the peak transverse-plane moment and hip work while walking straight and in both directions of the circle walking trials while wearing the study prostheses. This data will be processed (Visual3D; C-Motion, Germantown, MD) and aggregated using project specific software (Matlab; Mathworks, Natick, MA).

We hypothesize that:

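### The SAP drops the protocol's three Friedman tests of satisfaction for reasons that bear on power, not validity, so H2 gets no inferential answer

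*SAP*

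**What the plan says.** Protocol section 3.0 lists two general hypotheses under Aim 1. The second, H2, is that "an amputee preferred coupling ratio will exist within this range", meaning between no coupling and 1:2. Section 5.5 (Part 1, Visits 1 and 2) has the five settings tested in random order, with a rating of each: "Once we have enough data, participants will be asked to rate their satisfaction with the setting on a 0-10 scale".

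Section 5.6 splits H2 into straight walking (H2.1), prosthesis on the inside of the circle (H2.2) and prosthesis on the outside (H2.3). On analysis it says:

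- "Satisfaction data from the experiment will be tabulated for straight and both directions of the circle walking trials", at the five ratios.
- "The statistical analysis to test these hypotheses (H2.1, H2.2, and H2.3) will require three Friedman analyses of variance (ANOVA".
- The experiment-wise level is 0.05 and "a Bonferroni adjustment will be applied for multiple comparisons". No divisor is given. Exact p-values are promised for each test; intervals are not mentioned.
- The coupling ratio is chosen from the rank average of the torque results. Only if that cannot separate the ratios, "a similar method will be used to rank the results from hypothesis 2".

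The SAP, dated 23 September 2025 and written in the past tense, describes mixed models, F-tests and pairwise comparisons by coupling ratio. Its last sentence of method reads: "Statistical analysis on satisfaction results were not performed due to the small sample size and the higher expected variances in qualitative data". It describes no replacement analysis of satisfaction.

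**The concern.** H2 is one of the two hypotheses of Aim 1, and the protocol named its test in advance. The SAP withdraws that test on two grounds, sample size and expected variance. If either made a Friedman test misleading, withdrawal would be sound. If they only make it insensitive, the usual course is to run it, report it and caution against over-reading a null result.

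Without a test, a reader of tabulated ratings cannot judge whether an apparent favourite among five settings exceeds chance. The SAP also gives neither the n nor the SD on which its reasons depend, so the reader cannot weigh them.

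**Working it through.** **The plan's own figure.** H2 has no power statement. The only one for Aim 1 is for torque (H1.1): difference 19%, SD 17%, n = 15, power 98%. A paired two-sided t-test has d = 19/17 = 1.118, noncentrality 1.118 × √15 = 4.33 and power 0.980, so the figure reproduces. It says nothing about satisfaction.

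**Why the two reasons do not affect validity.** With k = 5 settings, r_ij the within-participant ranks and R_j their sums, the tie-corrected statistic is

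Q = (k−1) Σ_j (R_j − n(k+1)/2)² / Σ_ij (r_ij − (k+1)/2)².

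A participant's general level of rating cancels in the ranking, so between-participant spread does not enter. More within-participant noise makes the ranks more random, which costs power. Because the setting order is randomised, a permutation p-value is valid at any n.

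**Type I error of the chi-square version (4 df).** 20,000 simulated trials per n; ratings rounded to 0-10 with ties; assumed between-participant SD 2 and within-participant SD 1.5.

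| n | nominal 0.05 | nominal 0.0167 |
|---|---|---|
| 3 | 0.017 | 0.000 |
| 5 | 0.036 | 0.006 |
| 8 | 0.042 | 0.010 |
| 10 | 0.044 | 0.011 |
| 15 | 0.048 | 0.014 |
| 40 | 0.048 | 0.015 |

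The test is conservative at small n and never exceeds nominal.

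**Where the chi-square version fails to be useful.** The largest possible Q is n(k−1) = 4n. At n = 3, Q = 12 and p = e^(−6) × (1 + 6) = 0.0174, just above 0.05/3 = 0.0167, so it cannot reject. At n = 4, Q = 16 and p = e^(−8) × (1 + 8) = 0.0030. The exact untied test at n = 3 can reach 1/120² = 0.00007.

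**Power.** All inputs are assumed: threshold 0.05/3; participant mean 5 and SD 1.5; residual SD 1.5 / 2.0 / 3.0; 3-point peak pattern (0, 1.5, 3, 1.5, 0).

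| n | chi-square | permutation |
|---|---|---|
| 5 | 29 / 12 / 4% | 44 / 22 / 7% |
| 15 | 99 / 84 / 39% | 99 / 86 / 40% |

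For a 2-point peak the permutation test has 17 / 8 / 4% at n = 5 and 73 / 41 / 15% at n = 15. At the protocol's Part 1 ceiling of 40, with one setting one within-participant SD above the others, the chi-square test has about 96% power at 0.05/3. The SAP does not say where in this range the trial fell.

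**What the omnibus test can show.** With SD 2, a steady rise from 0 to 3 points rejects almost as often as the 3-point peak: 20% against 22% at n = 5, and 53% against 59% at n = 10 (permutation). A rejection says that some ratings differ, not which ratio is preferred.

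**Precision.** The unadjusted 95% half-width for a paired difference is t(0.975, n−1) × √2 × SD / √n. For SD 1.5 to 3.0 this is 2.6 to 5.3 points at n = 5 and 1.2 to 2.3 points at n = 15. Multiplicity-adjusted intervals are wider.

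**The case against.** The strongest reply is that the omission is disclosed with a reason, and that at n = 3 to 5 the test has so little power that leaving it out is defensible. The low power is real if n was that small, but the SAP does not give n. Disclosure of the omission also stops short of saying that section 5.6 had planned the tests.

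A second reply concerns the tests run on the other outcomes ("Pairwise hypothesis testing was carried out with adjustments for multiple comparisons"). It is tempting to say that these prove small n was no obstacle. That comparison is weak. The gait outcomes come from roughly three to six walks per setting, whereas satisfaction appears to be a single rating after them. The number of participants may be shared, but the information per setting is not.

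Third, the three-test plan may not be fully workable. At Visit 2 both circle directions are walked before the setting is rated, so there may be only one circle rating per setting. H2.2 and H2.3 could then not be separated. This objection stands, and the fix allows for it.

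A reader might also infer that the chosen coupling ratio is compromised. The documents do not support that: satisfaction only breaks ties, by rank average, which needs no p-value. Nor do they show that the tests were dropped after the ratings were seen, since neither document dates the decision. Nor is a missing interval a broken promise, because the protocol promised tests and p-values only. The ratings may still be tabulated as section 5.6 says.

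**Conclusion.** The concern holds in a limited form. Three prespecified tests of H2 were not performed, for reasons that lower power but leave a within-participant rank test valid, and the SAP neither reports n nor names the departure. The consequence is confined to the H2 conclusion.

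The validity finding is firm: it follows from the form of the test, and simulated size stays at or below nominal from n = 3 to 40. The size of the loss is not known. Power ranges from nil (chi-square, n = 3) to near certainty (n = 15, SD 1.5, 3-point peak), and rests on assumed effects, SDs and sample sizes. The 0.05/3 threshold is also an assumption, since section 5.6 gives no divisor. This should be corrected, but it does not undermine the torque analyses.

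**What to change.** Run the planned Friedman tests on the ratings already collected, with exact or permutation p-values if n is small. Then replace the SAP sentence with text to this effect:

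> Satisfaction (0-10) was compared across the five coupling ratios with the Friedman tests planned in protocol section 5.6. We report the n for each test, satisfaction by ratio, and p-values judged with a Bonferroni adjustment using divisor [state]. Within-participant pairwise differences are given with multiplicity-adjusted 95% intervals, and no ratio is called preferred on the omnibus test alone. H2 was not powered; a non-significant result is not evidence of no preference.

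The divisor is 3 if the adjustment is across the three activities; the SAP should say so, because the protocol does not. If only one circle rating per setting exists, run one circle test and state that H2.2 and H2.3 could not be separated. Any planned test not run should be listed as a departure from section 5.6, with the reason and n.

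The cost is a short analysis of ratings the protocol already collects and a few sentences of text. At very small n the intervals will be wide and a null result uninformative, and the report should say so.
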